### 3.5 Secondary Endpoints

The secondary endpoints of this study are as follows:

- The determination of PK parameters including half-life ( $t_{1/2}$ ), maximum serum concentration determined directly from the concentration-time profile ( $C_{max}$ ), observed time of peak plasma concentration ( $T_{max}$ ), area under the serum concentration-time curve from pre-dose ( $time_0$ ) to 24 hours post-dose ( $AUC_{0-24}$ ), and area under the serum concentration-time curve from pre-dose ( $time_0$ ) to infinity ( $AUC_{0-\infty}$ ), (Cohort 1); maximum plasma concentration determined directly from the concentration-time profile ( $C_{max}$ ) and  $T_{max}$  (Cohort 2 onwards) summarized by cohort and timepoint
- The evaluation of PD biomarkers based on absolute serum levels and percent change from baseline in serum levels of total immunoglobulin G (IgG), IgG subtypes (IgG1-4), immunoglobulin A (IgA), immunoglobulin M (IgM), albumin, and CIC summarized by cohort and timepoint
- The assessment of pemphigus disease activity by responses on PDAI based on absolute and percent change from baseline will be summarized by cohort and timepoint
- The assessment of pemphigus disease pathogenic antibody levels based on absolute and percent change from baseline of serum anti-desmoglein 1 and 3 antibody (anti-Dsg 1 and anti-Dsg 3) levels that will be summarized by cohort and timepoint
- The immunogenicity of once-weekly administered SYNT001 as determined by presence of anti-SYNT001 binding antibodies and neutralizing antibodies summarized by cohort and timepoint

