## 6. STUDY POPULATION

### 6.1 Target Population

This study will be conducted in approximately 20 male and female subjects aged 18 and older with a confirmed diagnosis of pemphigus (vulgaris or foliaceus).

Up to 8 subjects may be enrolled in Cohort 1. Four subjects will be enrolled sequentially in Cohort 2, 3, and 4 (optional cohort). An additional 4 subjects may be enrolled in Cohorts 2, 3 and 4 (optional cohort) following DEC's evaluation and recommendation.

Subjects who withdraw for any reason other than an AE and who do not receive study drug or have only received one dose of study drug may be replaced, up to one subject per cohort. Thus, the maximum number of subjects who may be enrolled in this study is 36 (20 + up to 12 additional subjects, + up to 4 replacements, as necessary).

Within Cohort 1, no more than 3 subjects may be enrolled with pemphigus foliaceus. Within successive cohorts,  $\leq 2$  subjects with pemphigus foliaceus may be enrolled.

Subjects will be enrolled only once in the study and will not be included in subsequent dosing cohorts. Subjects who do not receive all doses of study drug will continue to be followed through all scheduled visits.

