### 6.2 Inclusion Criteria

A subject must meet the following criteria to be eligible for the study:

1. Willing and able to read, understand, and sign an informed consent form.
2. Male or female  $\geq 18$  years of age at the time of screening.
3. Documented diagnosis of pemphigus vulgaris or foliaceus based on all 3 of the following criteria:
  - a. Documented clinical history consistent with pemphigus vulgaris or foliaceus (clinical presentation defined as mucosal and/or skin lesions).
  - b. Presence of Anti-Dsg 1 or 3 antibodies above the upper limit of normal (ULN).
  - c. History of at least one positive tissue-based test (eg, biopsy, direct immunofluorescence [DIF]).
4. Active disease defined as lesions lasting  $> 2$  weeks, and 3 active lesions in skin or mucosa or 2 active lesions with at least one being a skin lesion  $> 1$  cm diameter:
  - a. If treated with rituximab or other anti-CD20 mAb, last dose  $> 12$  months prior to screening.
  - b. If being treated with other immunosuppressants (ie, azathioprine, mycophenolate mofetil, methotrexate, dapsone, cyclosporine, tacrolimus, sirolimus, or low-dose cyclophosphamide [ $\leq 100$  mg/day]), dose must be stable, defined as  $< 25\%$  change in dose, for 4 weeks prior to screening.
  - c. On stable dose of corticosteroids, defined as  $\leq 1$  mg/kg of prednisone or equivalent and may not be increased by more than 50% in the 2 weeks prior to screening.

- d. Allowed topical therapies for pemphigus lesions upon entering the study include petroleum jelly or Aquaphor® for the skin or chlorhexidine for the mouth.
  - e. Stable use of topical low strength hydrocortisone ( $\leq 1\%$ ), tacrolimus, sirolimus, or pimecrolimus for lesions contributing  $< 10\%$  of the PDAI total activity score for the 4 weeks prior to screening is allowed. Stable use of dexamethasone elixir solution (swish and spit only) for oral lesions for the 4 weeks prior to screening is allowed.
  - f. If not on regular corticosteroids, no pulse corticosteroids are allowed in the 2 weeks prior to screening.
5. Body mass index (BMI)  $> 18.5$  kg/m^2.
  6. Has a negative pregnancy test documented prior to the first dose of study drug (for women of childbearing potential).

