### **11.2 Study Populations**

Three populations will be employed in the analysis of study data:

- The **Safety** population will consist of all subjects who have received at least one dose of study drug.
- The **PD** population will consist of all subjects who receive at least one dose of study drug and have post-dose PD data available.
- The **PK** population will consist of all subjects who receive at least one dose of study drug and have post-dose PK data available.

Primary safety analyses will be performed on the safety population. Demographics, subject disposition, screening, and baseline characteristics will be summarized for the safety and PD/PK populations, where appropriate.

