## 11.4.2 Statistical Methodology

All clinical data captured will be provided in data listings. Subject disposition, demographic information, and baseline characteristics will be presented. Baseline will be defined at the last value obtained prior to the first dose of study drug. Results will be summarized by dose level and cohort. Any discrepancy between treatment to be given and treatment received will be accounted for in these displays.

Continuous data will be summarized using descriptive statistics: number of subjects (N), number of observations (n), mean, median, standard deviation (SD), minimum, and maximum.

Categorical data will be summarized using frequencies and percentages. When categorical data will be presented, the percent will be suppressed when the count is zero to draw attention to the non-zero counts. The denominator for all percentages, unless otherwise specified, will be the number of subjects in the specified analysis population.

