##### **11.4.4.2 Pharmacodynamic/Activity Data**

The evaluation of PD biomarkers will be based on absolute and percent change from baseline in serum levels of total IgG, IgG subtypes (IgG1-4), immunoglobulin A (IgA), immunoglobulin M (IgM), albumin, and CIC that will be summarized by cohort and timepoint.

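### Percent change in anti-Dsg 1 and anti-Dsg 3 is summarised by cohort without restriction to subjects positive for that antibody at baseline, so the cohort mean can be diluted

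*Protocol*

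**What the plan says.** Four parts of the Protocol bear on this.

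- **Entry (Section 6.2, criterion 3b, repeated in the Synopsis):** "Presence of Anti-Dsg 1 or 3 antibodies above the upper limit of normal (ULN"). Either antibody is enough, so a subject positive for only one is eligible by design.
- **Endpoint (Section 3.5):** "absolute and percent change from baseline of serum anti-desmoglein 1 and 3 antibody", with "anti-Dsg 1 and anti-Dsg 3) levels that will be summarized by cohort and timepoint". The unit of summary is the cohort at a timepoint, and no subset is named.
- **Population (Section 11.2):** the PD "population will consist of all subjects who receive at least one dose of study drug and have post-dose PD data available". There is no condition on baseline antibody status.
- **Default summary (Section 11.4.2):** continuous data are described by "number of subjects (N), number of observations (n), mean, median, standard deviation (SD), minimum, and maximum".

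The PD paragraph in Section 11.4.4.2 covers "absolute and percent change from baseline in serum levels of total IgG, IgG subtypes (IgG1-4), immunoglobulin A (IgA), immunoglobulin M (IgM), albumin, and CIC". Anti-Dsg is not in that list, and no other paragraph of Section 11.4.4 mentions it. Table 8 in Section 7.5.5 schedules both titers at screening, Day 0 and later visits in Cohorts 1 to 3.

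**The concern.** The entry rule and the endpoint do not match. The entry rule expects some subjects to be positive for one antibody only, while the endpoint reports percent change in both antibodies for the whole cohort. For a subject at or below ULN for an antibody, percent change in that antibody says little about the drug's effect on disease-related autoantibody. There may be little to reduce, and ordinary assay variation is divided by a small baseline.

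Section 3.5 presents these antibodies as the pathogenic ones, and Section 2.2 anticipates that they will fall about as far as total IgG. A diluted mean could suggest that autoantibody falls less than IgG when it does not. Cohorts are also small: "Up to 8 subjects may be enrolled in Cohort 1", and four subjects are planned for each of Cohorts 2, 3 and 4, with up to four more after Dose Escalation Committee (DEC) review. The number of single-positive subjects may differ between cohorts, so part of a difference in mean percent change could reflect who was enrolled.

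**Working it through.** The Protocol gives no expected figure for anti-Dsg, and Section 11.3 states that no formal sample size calculation was done. There is therefore no stated result to reproduce. The check has two steps.

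**Step 1: does the text let antibody-negative subjects in?** Criterion 3b admits them, the Section 3.5 endpoint covers both antibodies in every cohort, the PD population has no antibody condition, and the default summary applies to all available values. The reduced-denominator rule in Section 11.4.1 concerns missing data, and a measured low titer is not missing. So they enter.

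**Step 2: how far can the mean move?** Let n be the cohort size, k the number negative for the antibody, p the percent change in positives and m that in negatives:

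mean = [(n - k) × p + k × m] / n

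Cohort sizes of 4 and 8 come from Section 6.1. The values of p, m and k are assumptions, because the Protocol gives none.

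*Dilution, m = 0%, p = -60%:*

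| n | k | Mean | Median |
|---|---|---|---|
| 4 | 1 | (3 × -60)/4 = -45% | -60% |
| 4 | 2 | (2 × -60)/4 = -30% | -30% |
| 8 | 1 | (7 × -60)/8 = -52.5% | -60% |
| 8 | 2 | (6 × -60)/8 = -45% | -60% |
| 8 | 3 | (5 × -60)/8 = -37.5% | -60% |

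Over a range of p, with n = 4 and k = 2, the mean is -20% for p = -40% and -35% for p = -70%.

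*Noise, one negative subject with an apparent rise, the others at -60%:* a rise of 100% gives (3 × -60 + 100)/4 = -20% at n = 4 and (7 × -60 + 100)/8 = -40% at n = 8. The median stays at -60% in both. The mean reaches zero only when the rise equals 60 × (n - 1), which is 180% at n = 4 and 420% at n = 8.

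*How often would this arise?* If a share q of subjects is negative for a given antibody, the chance of at least one in a cohort is 1 - (1 - q)^n. For assumed q of 0.10, 0.25 and 0.50 this is 34%, 68% and 94% at n = 4, and 57%, 90% and 99.6% at n = 8.

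The median results depend on giving all positives the same change. With varied responses the median would shift somewhat, but it would stay within the range of the positives' values while fewer than half the cohort is negative (for m above all of those values).

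**The case against.** The best case against this is that the Protocol fixes no wrong rule. Section 3.5 says only that levels are summarised, and averaging over every subject is inferred from the general defaults in Sections 11.2 and 11.4.2. Section 11.4.1 leaves detailed methods to a SAP, which was not available for this review and may modify the plan, so one cannot say that nothing later corrects this. Absolute change is reported as well. The default summary includes the median, minimum and maximum, and listings would show each antibody-negative subject in cohorts this small.

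All of that stands, and it limits the weight of the point. It does not remove the mismatch, because the entry rule, the endpoint and the population are all Protocol text and, applied as written, give the diluted mean.

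A reader might also infer three stronger things that the documents do not support:

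- **That antibody-negative subjects will reverse the result.** Reversal needs an apparent rise above 180% in one subject of four, or above 420% in one of eight, on the assumed -60%. The Protocol gives no assay floor or variability that would make such rises likely.
- **That these subjects have a baseline near zero.** The criterion refers to ULN, and a value below ULN can still be measurable and can fall on treatment. The 0% assumption is then pessimistic.
- **That dose selection is distorted.** Sections 3.4 and 11.4.3.2 base it on total IgG nadir and PDAI response. The DEC's inputs in Table 5 and Section 9.5.1 are open-ended lists of safety, PD and clinical data, with IgG as the named PD measure. Anti-Dsg appears in none of them.

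**Conclusion.** The point holds as a modest, inexpensive improvement to a descriptive secondary endpoint. The endpoint and population as written allow subjects at or below ULN for an antibody to enter its percent change, and in cohorts of four to eight this can dilute the mean materially. On the assumed -60% and 0%, one negative subject in four brings the mean to -45% and two bring it to -30%. The actual size is unknown, since the Protocol gives neither the number of single-positive subjects nor the expected change. The median, the absolute change and the listings offer partial protection, and no test, threshold or dose rule depends on anti-Dsg. Separately, and without any assumption, a named secondary endpoint has no entry in the analysis section.

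**What to change.** Three edits, in Sections 3.5 and 11.4.4.2:

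1. Summarise percent change for each antibody among subjects above ULN for that antibody at baseline, and show n for each antibody, cohort and timepoint. Baseline can be the last pre-dose value, as Section 11.4.2 already defines it.
2. Report absolute values and absolute change for all subjects in the PD population, so that nobody is dropped from view.
3. Add anti-Dsg 1 and anti-Dsg 3 to the Section 11.4.4.2 list.

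No new samples are needed, because both titers are already taken at screening and Day 0. The price is a smaller n per antibody, which in a cohort of four may leave only two or three subjects. Showing n makes that plain.

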### 3.6 Exploratory Endpoints

The exploratory endpoints of this study are as follows:

- The exploration of SYNT001 mechanisms of action and effects of SYNT001 on pathophysiology summarized by cohort and timepoint as determined by:
  - Complement component 3 (C3) levels by nephelometry
  - Anti-epithelial cell antibody (AECA) titers by indirect immunofluorescence
  - Fc gamma R2A receptor (*FCGR2A*) single-nucleotide polymorphisms (SNP) by genotyping
  - Presence of disease and inflammatory markers by RNAseq (RNA sequencing)
  - Immunophenotyping via measures of T cells, monocytes, NK cells and B cells by flow cytometry
  - Urine IgG levels to explore SYNT001 distribution and elimination

- Exploratory biomarkers to investigate immune response associated with pemphigus
- The evaluation of corticosteroid use during the study will be summarized by cohort and timepoint
- The assessment of SYNT001 impact on subject's HR-QoL by responses to the Autoimmune Bullous Disease Quality of Life (ABQoL) questionnaire and Skindex-29 scores summarized by cohort and timepoint
- The qualitative assessment of changes in appearance of skin and mucosal lesions as determined by photography presented by cohort and timepoint
- The determination of SYNT001 levels in skin biopsies across timepoints (skin biopsies optional)

Further details on the statistical and analytical plans for these endpoints are available in [Section 11](#).

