## 2. BACKGROUND AND RATIONALE

SYNT001, a humanized, affinity-matured IgG4-kappa monoclonal antibody (mAb), blocks immunoglobulin G (IgG) and circulating IgG immune complex (CIC) interactions with the neonatal crystallizable fragment receptor (FcRn), and inhibits the varied roles played by FcRn in the immune response.

Through specific and high affinity blockade of FcRn, SYNT001 has been shown to increase the catabolism of IgG and CIC in healthy volunteers and is predicted to block the ability of CIC to activate intracellular signaling events associated with binding to FcRn. This predicts that SYNT001 will also accelerate degradation of endogenous circulating IgG autoantibodies and IgG-IC specifically involved in the pathogenesis of autoimmunity. Blocking FcRn interactions with CICs further predicts that SYNT001 will have consequences for innate and adaptive cellular immunity. In the first instance, blocking multimeric CIC interactions with FcRn within antigen-presenting cells should result in inhibition of CIC inflammatory cytokine production and release by these cells. In addition, as FcRn determines the intracellular itinerary of CICs within and among compartments important in cellular immunity, it is further anticipated that SYNT001 will block antigen processing and presentation of antigens contained within CIC that otherwise lead to CD8+ and CD4+ T cell activation. Thus, SYNT001 is expected to specifically target immune functions associated with IgG and CIC that are involved in certain IgG-mediated autoimmune conditions.

SYNT001 targets key mechanisms contributing to pathology in a variety of IgG-mediated autoimmune disorders, including warm autoimmune hemolytic anemia (WAIHA) pemphigus, pemphigoid, myasthenia gravis, immune thrombocytopenic purpura (ITP), and chronic inflammatory demyelinating polyneuropathy (CIDP).

While current treatments for certain autoimmune disorders, including chronic steroids, immunosuppressants, intravenous immunoglobulin (IVIG), plasmapheresis, and anti-CD20 mAbs, such as rituximab, can be effective, they are associated with significant adverse effects, and delayed or non-durable responses.

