**Table 8. Pharmacodynamic Assessments**

Parameter	Collection Time Points		
	Cohort 1	Cohort 2	Cohort 3

 
IgG
 
IgG subtypes (IgG1-4)
 
IgA
 
IgM
 
	Screening and Days 0, 1, 2, 5, 7, 12, 14, 19, 21, 28, 29, 30, 33, 42, 56, 84, and 112	Screening and Days 0, 7, 14, 21, 28, 35, 42, 56, 84, and 112	Screening and Days 0, 7, 14, 21, 28, 35, 42, 49, 56, 63, 70, 77, 84, 91, 98, 105, 119, 147, and 175

 
Circulating immune complexes (CIC)
 
	Days 0, 5, 7, 12, 14, 19, 21, 28, 33, 42, 56, 84, and 112	Days 0, 7, 14, 21, 28, 35, 42, 56, 84, and 112	Days 0, 7, 14, 21, 28, 35, 42, 49, 56, 63, 70, 77, 84, 91, 98, 105, 119, 147, and 175

 
Albumin
 
	Screening and Days 0, 7, 14, 21, 28, 33, 42, 56, 84, and 112	Screening and Days 0, 7, 14, 21, 28, 35, 42, 56, 84, and 112	Screening and Days 0, 7, 14, 21, 28, 35, 42, 49, 56, 63, 70, 77, 84, 91, 98, 105, 119, 147, and 175

 
Anti-Dsg (1 and 3) antibody titers
 
	Screening and Days 0, 7, 14, 33, 56, 84, and 112	Screening and Days 0, 7, 14, 21, 28, 35, 42, 56, 84, and 112	Screening and Days 0, 7, 14, 21, 28, 35, 42, 49, 56, 63, 70, 77, 84, 91, 98, 105, 119, 147, and 175

 
C3 and AECA levels by indirect immunofluorescence
 
	Days 0, 14, 33, 56, 84, and 112	Days 0, 35, and 56	Days 0, 98, and 119

 
Exploratory biomarkers (RNAseq, urine IgG)
 
	Days 0, 14, 33, 56, 84, and 112	Days 0, 35, and 56	Days 0, 98, and 119

 
Immunophenotyping by flow cytometry for measurement of T cells, monocytes, NK cells, and B cells
 
	Days 0, 28, and 56	Days 0, 35, and 56	Days 0, 98, and 119

 
Exploratory biomarker (FCGR2A SNP, via buccal swab)
 
	Day 0	Day 0	Day 0

 
Exploratory pemphigus immune response biomarkers
 
	Days 0, 5, 7, 12, 14, 19, 21, 28, 33, 42, 56, 84, and 112	Days 0, 7, 14, 21, 28, 35, 42, 56, 84, and 112	Days 0, 7, 14, 21, 28, 35, 42, 49, 56, 63, 70, 77, 84, 91, 98, 105, 119, 147, and 175

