### 10.3.3 Potential Immune Effects

An antibody blocking FcRn is anticipated to have several effects. These include acceleration of catabolism of IgG, but not other immunoglobulin isotypes such as IgA and IgM, leading to dose-dependent decreases in circulating IgG levels by up to an estimated 50% from the baseline levels after a single dose and further decreases after multiple doses up to a 70% to 80% reduction. Based on studies in humans, it is expected that with a single dose, the nadir of this effect will

occur approximately 5 days after dosing. The time course of recovery of IgG following dosing in the Phase 1a study suggests that a return to within 30% of baseline levels observed at pretreatment occurs within 4 weeks after a single dose and within 4 weeks after multiple doses as shown in NHPs.

Given the normal adult range of total IgG of 500 to 1600 mg/dL (Agarwal and Cunningham-Rundles, 2007; Furst, 2009; Gonzalez-Quintela et al., 2008; Jolliff et al., 1982; Keystone et al., 2007; McMillan et al., 1997; van Vollenhoven et al., 2013), with a mean of 1150 mg/dL, a 50% decrease in the mean would be to 575 mg/dL and a 50% decrease from the low end of the normal range used for the inclusion criteria of 600 mg/dL in this study would be to 300 mg/dL. An 80% decrease from baseline after multiple doses would result in IgG levels of 230 mg/dL and 120 mg/dL, respectively. While these levels are in the range found in patients with primary humoral immunodeficiency (Ameratunga et al., 2013), the levels will be transient. Further, as reported for other therapies used for pemphigus, the temporary (ie, less than 4 months) depletion of IgG (up to 95% reduction of total IgG as seen with immunoadsorption) does not appear to impart an increased risk of infection (Eming and Hertl, 2006; Furst, 2009; Keystone et al., 2007; Schmaldienst et al., 2001; van Vollenhoven et al., 2013). Study subjects will be monitored clinically for any infection. Further, commercial IVIG can be given to reverse the low IgG levels in case of a bacterial infection occurring while their IgG levels are decreased.

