### **11.3 Sample Size Justification**

Formal sample size calculations were not performed. The number of subjects was chosen based on feasibility and was considered sufficient to meet the study objectives.

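### The exploratory urine IgG endpoint cannot show how SYNT001 itself is distributed or eliminated; as planned it can only mark how IgG is handled

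*Protocol*

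**What the plan says.** Section 3.6 of the protocol, and the matching row of the Synopsis, give the endpoint as "Urine IgG levels to explore SYNT001 distribution and elimination". It sits under a parent item on mechanism of action and effects on pathophysiology. Table 8 (Section 7.5.5) places it among the pharmacodynamic assessments, in the row that begins "Exploratory biomarkers (RNAseq, urine IgG".

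The collection days in that row are:

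- Cohort 1: "Days 0, 14, 33, 56, 84, and 112"
- Cohort 2: "Days 0, 35, and 56"
- Cohort 3: "Days 0, 98, and 119"

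Section 2 describes the drug as "SYNT001, a humanized, affinity-matured IgG4-kappa monoclonal antibody (mAb". Section 10.3.3 expects blockade of FcRn to cause "acceleration of catabolism of IgG, but not other immunoglobulin isotypes such as IgA and IgM", with a 70% to 80% fall in IgG after repeated doses. The primary dose-selection endpoint in Section 3.4 looks for a nadir 60% to 90% below baseline.

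The drug itself is measured elsewhere: in serum (Sections 3.5 and 7.5.4, with half-life and AUC in Cohort 1) and in optional skin biopsies (Section 3.6).

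**The concern.** The endpoint assigns the disposition of the drug to an analyte that is not the drug. The schedule and assessment sections call it simply urine IgG; none names a SYNT001 assay in urine or a urine IgG4 measurement. The treatment is meant to remove most of the subject's own IgG, so urine IgG can be expected to move with serum IgG. A drop on treatment and a recovery afterwards would appear whether SYNT001 were cleared by the kidney or by another route.

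The timing adds to the difficulty. The samples are taken days after an infusion, and all but one lack a same-day drug concentration in serum to set beside them.

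What is at stake is the interpretation of one exploratory result. Under its present label, a change caused by the intended loss of IgG could be read as information on elimination of the drug.

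**Working it through.** There is no planned figure to reproduce. Section 11.3 says "Formal sample size calculations were not performed", and the endpoint is descriptive.

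**1. Time from the last infusion to each urine sample**

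Infusion days are 0, 7, 14, 21 and 28 in Cohorts 1 and 2, and weekly from Day 0 to Day 91 in Cohort 3 (Tables 2 to 4). Day 0 urine is collected before the first dose (Section 8.1.2). Gap = urine day minus the last preceding infusion day.

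| Cohort | Last infusion | Urine day | Gap (days) | Serum PK that day |
|---|---|---|---|---|
| 1 | 7 | 14 (pre-dose, Section 8.2.6) | 7 | no |
| 1 | 28 | 33 | 5 | yes |
| 1 | 28 | 56, 84, 112 | 28, 56, 84 | no |
| 2 | 28 | 35, 56 | 7, 28 | no |
| 3 | 91 | 98, 119 | 7, 28 | no |

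The shortest nominal gap is 5 days. In Cohorts 2 and 3, the one-day windows at both visits let the 7-day gap run from 5 to 9 days. Serum IgG, by contrast, is scheduled on every urine IgG day (Table 8).

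**2. Change in urine IgG expected from the fall in own IgG alone**

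Assume urine IgG is proportional to serum IgG, that is, renal handling is unchanged. Fold fall = 1/(1 − r), where r is the fractional fall in serum IgG.

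- Target in Section 3.4: 1/(1 − 0.60) = 2.5 and 1/(1 − 0.90) = 10.
- Expectation in Section 10.3.3: 1/(1 − 0.70) = 3.3 and 1/(1 − 0.80) = 5.

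These sizes apply to samples near the nadir. They contain no information on the drug's route of elimination.

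**3. How much of the measured IgG could be drug**

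If the assay does not detect SYNT001, the share is zero. If it does, take serum share as a stand-in for urine share:

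share = Cd/(Cd + own IgG), with Cd = (dose/45 mL/kg) × 1/(1 − 2^(−7/h)) × 2^(−t/h)

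The 45 mL/kg plasma volume and the half-life h of 0.5 to 5 days are assumptions; the protocol gives neither. Own IgG of 230 mg/dL is the protocol's figure for an 80% fall from the mean of 1150 mg/dL (Section 10.3.3).

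Example at 45 mg/kg, h = 5 and t = 5: dose/45 mL/kg = 100 mg/dL; accumulation 1/(1 − 0.379) = 1.61; decay 0.5; Cd = 80.5 mg/dL; share = 80.5/(80.5 + 230) = 26%.

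| Dose | h = 2, t = 5 | h = 5, t = 7 to 5 |
|---|---|---|
| 10 mg/kg | 1.8% | 6% to 7% |
| 30 mg/kg | 5.3% | 15% to 19% |
| 45 mg/kg | 7.8% | 21% to 26% |

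Shorter half-lives give smaller shares. The drug reaches half of the total only at 45 mg/kg with h = 5 and own IgG of 60 mg/dL (90% below the 600 mg/dL entry floor), where the share is 50% to 57%. That dose belongs to the optional Cohort 4, which has no urine schedule in Table 8.

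**4. Urine dilution**

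Table 7 lists creatinine under serum chemistry only and specific gravity under urinalysis. Urinalysis is done at all the urine IgG visits. The protocol does not link either to urine IgG. If specific gravity ranged from 1.005 to 1.030 (an assumption), an uncorrected concentration could vary 0.030/0.005 = 6-fold through hydration alone; for 1.010 to 1.025 the factor is 0.025/0.010 = 2.5.

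**The case against.** The best defence is that this is one phrase in an exploratory endpoint on which no dose decision or safety rule depends. The parent item concerns mechanism, and Table 8 already treats urine IgG as pharmacodynamic. Elimination is covered by Cohort 1 serum half-life and AUC, and tissue distribution by the skin biopsies. All of that stands, and it keeps the point small.

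It also rules out several stronger readings that a reader might infer:

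- *That urine IgG tells us nothing about the drug.* The drug acts by changing IgG catabolism, so urine IgG can reflect its effect on IgG handling. What it cannot show is the drug's own disposition.
- *That results are uncorrected for dilution.* The protocol states no correction, but it does not exclude one. Specific gravity is measured at these visits, collection detail is left to a laboratory manual that is not shown, and nothing says the specimens are spot urines.
- *That the samples miss the drug, or always contain mainly own IgG.* Both depend on a half-life the protocol does not give. The protocol itself draws serum PK 5 days after dosing, and under extreme assumptions the drug share is large.
- *That the trial's account of elimination would be misleading.* Serum PK supplies that account, independently of urine.

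The defence does not rescue the stated purpose. Analyte, purpose and collection days are fixed in the protocol, and an analysis plan cannot extract drug disposition from an IgG measurement that does not separate drug from own IgG.

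**Conclusion.** The point holds, at low severity. Urine IgG as specified cannot show the distribution or urinary elimination of SYNT001. This follows from the protocol alone: no drug-specific urine assay is named, the drug is an IgG4, own IgG is meant to fall by 60% to 90%, and only one post-baseline urine visit is paired with serum PK.

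The size of the confounding change, 2.5- to 10-fold near the nadir, rests on unchanged renal handling. The drug-share figures rest on an assumed half-life and plasma volume, and on serum standing in for urine; they illustrate the problem but the conclusion does not depend on them. The measure is still worth keeping as a marker of IgG handling. No primary or secondary conclusion is affected.

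**What to change.** - Reword the endpoint in Section 3.6 and the Synopsis as urinary IgG loss, and drop the reference to the drug's distribution and elimination.
- State how dilution is handled: either the ratio of IgG to creatinine in the same specimen, or adjustment by the specific gravity already measured at these visits.
- Report the result beside the same-day serum IgG, which is already scheduled on every urine IgG day.
- If urinary elimination of the drug is wanted, name a SYNT001-specific urine assay. Among existing samples, Cohort 1 Day 33 is the only post-baseline one with serum PK on the same day.

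The first and third changes cost a line of text each. The second costs at most a urine creatinine on specimens already planned. A drug-specific urine assay would be an additional cost, needed only if the sponsor wishes to keep the elimination question.
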